#### **8.8 Clinic follow up (standard of care)**

The chart will be reviewed for infections missed on phone calls.

### **9.0 RISKS TO HUMAN SUBJECTS**

Each patient will be consented prior to treatment and appropriate IRB and HIPAA guidelines will be followed. The selection of antibiotics can vary with treating physician if the urine test is negative. In some cases during the study, the treating physician will receive additional information and choose an antibiotic based on the data rather than their personal preference. Alternatively, the treating physician may choose to select their personal preference despite the additional information provided, as the treating physician will select the best antibiotics for the subject. The American Urological Association best practice statement will be included to the ID Pharmacist and treating physician to ensure that guidelines are met.

No adverse events are anticipated as this is a minimal risk study. Participation in this study is completely voluntary and will not affect their healthcare in any way. The alternative to this study is to not participate. Separately, any risks associated with the standard of care transurethral procedure will be discussed and outlined with the treating physician and medical team.

Each provider will consent before initiation of research procedures. Providers will be informed that the data collected from them will not be used for purposes outside of the research and that their decision to participate or not participate will not positively or negatively affect their standing as UTHSA employees and their participation is voluntary. No identifiable information will be collected from providers. Providers are to follow best practices when prescribing and select what they believe is best for the subject.

### **10.0 METHOD OF ANALYSIS/STATISTICS**

**Next Generation Sequencing:** Standard of care whole urine will be collected (approximately 30-50 mL) utilizing special vacutainers supplied by MicroGen Dx. Approximately 5-10mL of urine taken for culture will be sent to MicroGen Dx, a CAP-accredited and CLIA licensed clinical diagnostic lab, for analysis. MicroGen Dx will perform rapid PCR for common resistance genes prior to ureteroscopy or percutaneous nephrolithotomy. The plan will be to run target bacterial or fungi DNA on the quantitative PCR (qPCR) panel assay on the Roche LightCycler 480 II instrument and sequencing of 16S ribosomal RNA hypervariable regions V1-V2 using Ion Torrent (Ion Torrent PGM).

**Microbiome:** Sequencing reads were demultiplexed using QIIME2 software and denoised using dada2 software, using a phred score threshold of 28. Alpha diversity will be measured using the Shannon index, and a Wilcoxon test was used to determine whether the Shannon index differed between patients with stents and those without stents at the time of urine collection. Principle coordinates analysis (PCoA) of Bray-Curtis dissimilarity will be performed to visualize differences in species composition between patients with and without stents, and Linear discriminant analysis Effect Size (LEfSe) analysis was conducted to identify differentially abundant taxa between stent and non-stent groups.

**Sample size:** This will be a randomized trial of Microgen Dx versus standard of care. The primary endpoint is infection within 14 days of surgery. The primary objective of the study is to evaluate whether Microgen Dx reduces an infection rate compared to the standard of care. The null hypothesis is that infection rates within 14 days of surgery are the same between the randomization arms. The alternative hypothesis is that infection

rates within 14 days of surgery are not equal between the randomization arms. The infection rates are assumed to be 11% in the control arm and 1% in the experimental arm based on our preliminary data. A sample size of 85 per group will give 80% power to detect a 10% difference in infection rate when the two-sided Z-test with alpha=0.05 is used. Demographics and potential confounding factors will be summarized by randomization arm. A logistic regression model will be used to measure the association between the primary outcome and treatment arm with adjustment for the observed covariates.

**Statistical analysis:** Our primary outcome is infection after surgery as a dichotomous outcome. We will utilize a chi-squared analysis to determine the difference between intervention and control groups. We will assess demographics between groups using chi-squared for dichotomous variables and Student's t-test for continuous variables. Additionally, we will investigate the utilization of antibiotic in a mixed-model regarding a number of antibiotics and antibiotic class utilization.

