Subjects will be recruited from approved Urology clinics at time of their preoperative appointment, approximately 30 days, but up to 90 days, prior to the planned transurethral procedure. Patients with ureteral stents will not be excluded; therefore, essentially any patient going to surgery for percutaneous nephrolithotomy, ureteroscopy or other transurethral procedure, within two to four weeks will be screened for eligibility and approached for enrollment. In the event the standard of care urine culture was performed more than 45 days before the urologic procedure; the treating physician will ask the patient to provide an additional urine sample as part of normal practice. Research staff will obtain a second sample (5-10 mL) of left-over urine, which will then be sent to MicroGen Dx for analysis. If this occurs, the second sample will be used for analysis.

**Next Generation Sequencing:** Approximately 30-50 mL voided whole urine will be collected as per routine care. Approximately 5-10mL of left-over urine will be obtained for research, placed in special vacutainers supplied by MicroGen DX, a CAP accredited and CLIA licensed clinical diagnostic lab, and sent for analysis. MicroGen DX will perform rapid PCR for common resistance genes prior to transurethral procedure, such as ureteroscopy or percutaneous nephrolithotomy. NGS results will be available within 48-72 hours. Additionally, NGS analysis will be performed on available or leftover urinary stones for a proportion of the subjects.

Target bacterial or fungi DNA on the quantitative PCR (qPCR) panel assay on the Roche LightCycler 480 II instrument and sequencing of 16S ribosomal RNA hypervariable regions V1-V2 using Ion Torrent (Ion Torrent PGM) will be run.

**Data Collection:** Prior to and after surgery, patient medical history, demographics, pre and post-surgical antibiotic treatment plans, and speciation results from the urine culture will be collected by research staff. Results obtained from the NGS/PCR analysis report, such as resistance gene data, will be recorded. Recommendations from the ID pharmacist will also be recorded.

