## **8.3 Medical History/Demographics (research)**

Data collected will include demographics, medical history, to include but not limited to, medication and treatment history, laboratory and vitals results, diagnosis results, and procedure and surgical history.

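### The stent versus non-stent microbiome comparison states no error control across taxa and no covariate adjustment, so its taxon list is likely to include chance findings and may reflect other patient differences

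*Combined protocol and SAP*

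**What the plan says.** The Microbiome paragraph of Section 10.0 sets out three comparisons of stented and unstented patients.

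- Alpha diversity: "a Wilcoxon test was used to determine whether the Shannon index differed between patients with stents and those without stents".
- Composition: a principal coordinates plot of Bray-Curtis dissimilarity, which "will be performed to visualize differences in species composition between patients with and without stents". No test goes with it.
- Individual taxa: "Linear discriminant analysis Effect Size (LEfSe) analysis was conducted to identify differentially abundant taxa between stent and non-stent groups".

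The paragraph gives a read-quality threshold (phred 28) but nothing on inference. It states no number of taxa, taxonomic level, significance level, LEfSe effect-size cut-off, multiplicity procedure, covariate or stratum.

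Other sections do not fill these gaps. Section 4.0 says "Patients with ureteral stents will not be excluded", so stent status is a patient characteristic and not an allocated one. Covariate adjustment appears only in the logistic model for infection, which measures the "association between the primary outcome and treatment arm with adjustment for the observed covariates". Confounders are tabulated by arm and not by stent status: "Demographics and potential confounding factors will be summarized by randomization arm". Section 8.3 collects demographics and medical history, including "medication and treatment history, laboratory and vitals results, diagnosis results, and procedure and surgical history".

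The comparison belongs to none of the three aims in Section 3.0. Its nearest rationale is the hypothesis in Section 2.0 that a stone or an earlier stent may let bacteria form biofilms or escape standard culture.

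**The concern.** Two separate problems meet in one short paragraph.

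The first is multiplicity. A search for differing taxa tests each taxon, and the output is the list that passes. Without a stated error rate for the list, a reader cannot tell how much of it is chance. The ordination is descriptive, so no overall test stands in front of the list.

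The second is confounding. Patients with stents may differ from those without in ways that also affect the urine microbiome. The plan adjusts the randomised comparison of infection for covariates, but not this non-randomised comparison, which needs adjustment more.

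At stake is how the list is read. Given the biofilm hypothesis in Section 2.0, a table of stent-associated taxa could be taken as support for it. The test of infection by randomised arm is not touched.

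**Working it through.** **The plan's own figures.** The microbiome analysis has none. The only reproducible design figure is 85 per group for infection (Section 10.0: 11% versus 1%, two-sided 0.05, 80% power). With unpooled variance, n = (1.960 + 0.842)² × (0.11 × 0.89 + 0.01 × 0.99) / 0.10² = 84.6, which rounds up to 85. The figure reproduces and has no bearing on this point.

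**Multiplicity.** Assumed, because the plan gives none of them: m taxa tested, a per-taxon level of 0.05, independence, and no true stent difference in any taxon. The 0.05 in Section 10.0 belongs to the infection test.

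Expected false taxa = 0.05 × m. Chance of at least one = 1 − 0.95^m.

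| m (assumed) | Expected false taxa | Chance of at least one |
|---|---|---|
| 20 | 1.0 | 64% |
| 50 | 2.5 | 92% |
| 100 | 5.0 | 99.4% |
| 200 | 10.0 | >99.9% |

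The expected count does not need independence; the chance of at least one does.

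With Bonferroni (0.05/m per taxon), the chance of at least one false taxon is 4.9% at each m. With Benjamini-Hochberg at 5%, simulated 2,000 times each for m = 50, 100 and 200, it is 4.6%, 6.2% and 5.3%, that is, 5% within simulation error.

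**Confounding.** This was simulated with no stent effect at all. Assumed: 220 patients (2 × 110, from Section 8.4), 30% or 50% stented, and a binary covariate that shifts a taxon by 1 SD. Each setting had 2,000 runs at the 0.05 level. The unadjusted test is the Wilcoxon rank-sum test; the adjusted test is a linear model with stent and the covariate.

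| Covariate prevalence, stented vs unstented (assumed) | Unadjusted rejection | Adjusted rejection |
|---|---|---|
| 50% vs 50% | 5% | 4–5% |
| 60% vs 40% | 22–27% | 5% |
| 70% vs 30% | 69–77% | 4–5% |

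The inflation comes entirely from imbalance. With balance there is none.

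**What the documents say about imbalance.** They give no distribution of sex, site or antibiotic use by stent status. They do make some variation plausible. Section 7.0 recruits from three settings, one of them a Veterans hospital. Section 5.0 admits any transurethral procedure. Section 2.0 says that patients with positive cultures are treated before surgery. Under Section 4.0, a culture more than 45 days old leads to a second urine sample, which replaces the first in the analysis.

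**The case against.** A reader might infer that the analysis will list false taxa and will credit stents with differences caused by antibiotics or sex. The documents do not support that certainty.

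- **Taxon counts.** The number of taxa, the per-taxon level and independence are all assumed, and relative abundances are not independent. LEfSe also selects on an effect-size score, so 0.05 × m is not a forecast of the reported list. This stands: the table is an approximate upper guide under a complete null. The effect-size filter is still not an error rate, and the plan states no cut-off for it.
- **Sex and antibiotics.** No section shows either to be unbalanced by stent status, and none names sex as relevant to the urine microbiome. This stands: confounding is possible but not shown.
- **Timing.** The sequenced urine is left over from the culture specimen, so treatment directed by that culture comes after a first sample. Only a repeat sample could follow it; earlier courses are possible but not described. If stents lead to colonisation and then to treatment, antibiotics lie on the pathway, and adjusting for them changes the question. This stands, and it argues for a sensitivity analysis instead of a main adjustment.
- **Status.** The comparison is outside the aims and carries no confirmatory claim. Replacing a valid two-group Wilcoxon test or LEfSe outright, or requiring an overall test as gatekeeper, would be partly preference. This stands too.
- **Tense.** The Wilcoxon and LEfSe steps are in the past tense and the ordination in the future. The text might come partly from completed work such as the 20-patient pilot in Section 2.0, but that cannot be confirmed.

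None of this supplies an error rate for the list or an adjusted estimate for a non-randomised contrast.

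**Conclusion.** The point holds as a minor one about an exploratory analysis. Followed as written, the plan gives a taxon list with no stated error control from an unadjusted, non-randomised comparison.

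Chance findings are likely in that list: 1 to 10 expected false taxa for 20 to 200 tested. That range assumes a complete null and a 0.05 level; the 64% to over 99.9% chance of at least one also assumes independence. Both are approximate upper guides.

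Confounding by recent antibiotics, sex or site may add to the list. The simulated rejection rates of 22% to 77% apply only under the assumed imbalances and a 1 SD covariate effect. The documents establish neither.

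A reader might also fear for the primary result. Infection is tested by randomised arm in a separate analysis, so its type I error is unaffected.

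**What to change.** In the Microbiome paragraph of Section 10.0:

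1. Label the stent comparison exploratory, and state whether it is planned or already done and on which patients.
2. State the taxonomic level, the per-taxon significance level and the LEfSe effect-size cut-off.
3. Report per-taxon results at a Benjamini-Hochberg false discovery rate of 5%.
4. Keep the Wilcoxon and LEfSe results, and report beside them an overall PERMANOVA on Bray-Curtis distance, a regression of the Shannon index on stent status, and per-taxon models. Adjust each for sex and site.
5. Add recent antibiotic use to those models as a sensitivity analysis only, and say that it may lie on the pathway from stent to microbiome.

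The cost is a few lines of wording and minor extra analysis. Demographics and medication history are already collected, so little or no new data should be needed. The downside is that fewer taxa will be declared. The primary endpoint and sample size do not change.

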### **3.0 SPECIFIC AIMS**

#### **Specific Aim 1: To perform a randomized clinical trial investigating the use of NGS for antibiotic selection to lower post-operative infection rates over the standard of care.**

*Hypothesis: utilization of NGS for the selection of preoperative antibiotics reduces postoperative infection rates by 75%. Our baseline rate of infection was 11-15% in our pilot study and nearly 5-10% in our investigation of those ureteroscopies (not PCNL, which has a higher rate) of infections at a university hospital. We expect with the correct antibiotics that the infection rate may drop from 11% to 1% or less. The control arm will be utilized to determine if NGS may have predicted infections or high-risk groups. Retrospective databases include anywhere from 2-15% of patients will present with a postoperative infection after transurethral surgery. Current prophylaxis strategies do not always follow guidelines, and with concerns over current non-reimbursement for infectious complications, surgeons may be using more antibiotics.*

**Specific Aim 2: Accuracy of NGS and PCR compared to standard urine culture prior to transurethral procedures.** *Hypothesis: NGS can identify 50% of negative urine cultures that could harbor uropathogenic bacteria.* We anticipate a substantial number of patients have uropathogenic bacteria present yet are not detected by traditional approaches. We seek to expand our investigation on this topic in order to understand how best to interpret the results and present them to physicians. All participants will have both a standard of care urine culture and NGS testing/ID Pharmacy review for comparative analysis. Only subjects assigned to the NGS group (n=110) will have NGS urine culture results and ID Pharmacist recommendations shared with the physician to determine antibiotic selection. Operating characteristics to include sensitivity, specificity, positive, and negative predictive value will then be performed and area under the receiver operative curve calculated. We will enroll a minimum of 250 patients and 5 urology provider-participants into this study. We anticipate that 20 of the patients will have positive urine cultures and 200 will have negative cultures. Of the 200 negative cultures we anticipate that 100 (50%) will harbor uropathogenic bacteria which will be identified via NGS.

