## **8.4 Randomization (research)**

A randomization list will be generated using a computer-based-random number generator [www.randomizer.org](http://www.randomizer.org). Randomization will be created 1:1, n=110 per group. Once created, individual envelopes will be created, and study staff will pull an envelope after the participant signs consent. The research staff will not be blinded to the randomization groups. The standard of care group will have urine culture results directed to treating physician. The intervention group will have NGS results sent to Infectious Disease pharmacist, [name] to provide an antibiotic recommendation. The antibiotic recommendation, along with NGS results, will then be provided to treating physician. The physician will then utilize these tools to select the best antibiotic for the case but is not required to abide by the ID pharmacist's recommendation. The standard of care group will have a urine sample sent to MicroGen Dx, but the results will not be provided to the physician.

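### At the planned 11% versus 1%, the adjusted logistic model has no finite treatment estimate in 22–33% of trials at 110–150 per arm; a Firth fit avoids this

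*Combined protocol and SAP*

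**What the plan says.** Section 10.0 of the combined protocol and SAP describes two analyses of the primary endpoint, infection within 14 days of surgery.

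- **Sample size paragraph:** "A logistic regression model will be used to measure the association between the primary outcome and treatment arm with adjustment for the observed covariates". The covariates are not listed, and no penalised, exact or other method is given for sparse events.
- **Statistical analysis paragraph:** "We will utilize a chi-squared analysis to determine the difference between intervention and control groups". This matches the two-sided Z-test used for sizing, so it appears to be the primary test.

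The planning assumption sits beside the logistic model: "The infection rates are assumed to be 11% in the control arm and 1% in the experimental arm". From it, "A sample size of 85 per group will give 80% power to detect a 10% difference in infection rate". Section 3.0, Aim 1, also hypothesises that NGS "reduces postoperative infection rates by 75" per cent, a smaller effect than 11% to 1%.

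The number to be enrolled varies across the document. Section 8.4 says "Randomization will be created 1:1, n=110 per group", and Aim 2 also has 110 in the NGS group. Section 8.0 has 250 completers (125 per arm). Section 1.0 has about 300 subjects (150 per arm). The figure of 85 per arm is the calculated minimum and is nowhere the planned enrolment.

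**The concern.** An infection rate near 1% in an arm of 110 to 150 patients makes zero infections a realistic result. With no NGS-arm infections, the logistic likelihood keeps rising as the treatment coefficient goes to minus infinity. The fitted odds ratio goes to 0, and the Wald standard error and interval lose their meaning. Covariates cannot restore a finite maximum.

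This happens most often when NGS works as well as the plan assumes. The report could then show a clearly significant chi-squared test beside an adjusted model whose printed Wald p-value is close to 1, with no rule for which to believe or how to repair the model. A remedy chosen at that point would be chosen after seeing the results by arm.

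**Working it through.** **1. Reproduce the plan's figure.** Two-sided alpha 0.05, 80% power, unpooled variance:

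n = (1.960 + 0.842)² × (0.11 × 0.89 + 0.01 × 0.99) / 0.10² = 84.6, rounded up to 85 per arm. The plan's number is confirmed. The pooled-variance version gives 88.

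**2. Expected NGS-arm infections at 1%.** 110 × 0.01 = 1.1; 125 × 0.01 = 1.25; 150 × 0.01 = 1.5. Both arms together: n × (0.11 + 0.01) = 13.2, 15.0 and 18.0.

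**3. Probability of no NGS-arm infection**, P = (1 − p)ⁿ. Aim 1's reduction gives p = 0.11 × 0.25 = 2.75%. The 2% column is an assumed in-between rate.

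| Per arm | p = 1% | p = 2% (assumed) | p = 2.75% |
|---|---|---|---|
| 110 | 33.1% | 10.8% | 4.7% |
| 125 | 28.5% | 8.0% | 3.1% |
| 150 | 22.1% | 4.8% | 1.5% |
| 85 (minimum only) | 42.6% | 18.0% | 9.3% |

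These are floors for the share of trials with a non-finite treatment coefficient, because sparse covariate patterns can only add to them. Aim 1 also allows for a rate below 1%; at an assumed 0.5% the range is 47–58% for 150 down to 110 per arm. A small simulation (400 trials per scenario, four assumed covariates unrelated to outcome, separation tested by linear programming) found non-finite treatment coefficients in the same share of trials as had no NGS-arm infection, in every scenario. Its shares differ from the table by sampling error (for example 27% against 33.1% at 1% and 110 per arm); the exact values are the ones to use.

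**4. Example: 0/110 versus 12/110, no covariates.**

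- Chi-squared: 220 × (110 × 12)² / (110 × 110 × 12 × 208) = 12.7, p = 0.0004.
- Ordinary logistic fit: log odds ratio −22.5, standard error 12,491, Wald p = 0.9986.
- Maximum-likelihood profile interval: odds ratio 0, upper limit 0.157.
- Firth: in a 2×2 table this amounts to adding one half to each cell, (0.5/110.5) / (12.5/98.5) = 0.036. Profile 95% CI 0.0003 to 0.28, p = 0.0001.
- Risk difference: 0 − 12/110 = −10.9 points, Miettinen-Nurminen 95% CI −18.1 to −6.3.

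**5. Does the Firth fit behave?** Exact enumeration of all 2×2 tables, no covariates, at 110/125/150 per arm:

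| Quantity | 11% vs 1% | 11% vs 2.75% |
|---|---|---|
| Coverage of 95% profile CI | 0.962/0.964/0.966 | 0.959/0.957/0.952 |
| True odds ratio | 0.082 | 0.229 |
| Geometric-mean Firth odds ratio | 0.094/0.091/0.087 | 0.229/0.229/0.228 |

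Type I error with 6% in both arms is 0.046/0.047/0.044. With two assumed binary covariates (30% prevalence, odds ratio 2 each; 1,500 simulated trials per cell), the Firth treatment estimate was finite in every trial. Coverage was 0.954/0.963/0.967 at 11% vs 1% and 0.960/0.959/0.953 at 11% vs 2.75%.

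**The case against.** The strongest reply is that little is at stake. Randomisation makes the unadjusted comparison unbiased, and the chi-squared test handles a zero cell. Most trials have no zero cell: 67–78% at 11% vs 1%, and 95–98.5% at the 75% reduction that Aim 1 states as its hypothesis. This stands, and it keeps the point below the level of a flaw in the primary analysis. It does not remove it: 11% vs 1% is the assumption on which the trial is sized, and an analysis should work in its own design scenario.

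Second, the plan does not commit to Wald intervals, and an ordinary profile interval still gives an upper limit (0.157 in the example). That is true and informative, but it leaves an odds ratio of 0 as the point estimate.

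Third, the printed −22.5 and 12,491 depend on the convergence tolerance: −18.5 and 1,690 at 1e-6, −27.5 and 152,176 at 1e-10. This too is correct. The exact values mean nothing, which is the difficulty with reporting them.

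Fourth, Firth is one option among several (exact logistic regression, a weakly informative prior). With zero events its point estimate and lower limit come from the penalty, and its upper limit of 0.28 is wider than 0.157. This is a fair caveat to state in the report, but not a reason to leave the method unnamed.

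Finally, the document does not name stent as an infection covariate, and the covariates in the simulations are assumed. Both are so. The zero-event probabilities depend on neither.

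**Conclusion.** The concern holds. At the plan's own 11% vs 1%, the adjusted model yields no finite treatment log odds ratio in at least 22–33% of trials at 150 down to 110 per arm. At an assumed 2% NGS rate the range is 5–11%, and at Aim 1's 75% reduction 1.5–5%, where the problem is uncommon. The figures are exact binomial probabilities and assume that the logistic model is fitted by ordinary maximum likelihood, the natural reading when nothing else is named.

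The harm is confined to the adjusted effect estimate and its standard interval. The chi-squared test and the primary conclusion are not affected. The plan should be changed because the failure is foreseeable, arises mostly when the intervention succeeds, and is cheap to prevent.

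**What to change.** Amend the logistic-regression sentence in Section 10.0 to state that:

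- the adjusted model is fitted by Firth penalised likelihood, with profile-penalised-likelihood 95% confidence intervals and test;
- it is supportive to the chi-squared test, which is the primary test;
- it includes only a few named baseline covariates that the protocol already recognises. Examples are PCNL versus other procedure (Aim 1 sets its ureteroscopy rate apart: "not PCNL, which has a higher rate") and ureteral stent present (Section 4.0: "Patients with ureteral stents will not be excluded"; Section 2.0 suggests stents may harbour organisms that culture misses). With 13 to 18 infections expected in total at 11% vs 1%, a longer list cannot be supported under any fitting method;
- the primary result is reported as the risk difference with a score-type 95% interval such as Miettinen-Nurminen, so that a usable effect size exists even with a zero cell.

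The cost is SAP wording, with no new data, visits or patients. The downsides are shrinkage of the odds ratio towards 1 (average 0.087–0.094 against a true 0.082 at 11% vs 1%, almost none at the 75% reduction) and adjustment for fewer covariates. Firth does not cure the low event count. When the NGS arm has no infections, the report should say that the lower limit reflects the penalty.
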